5.2. Statistical and Analytical Plans

5.2.1. General Considerations

All data will be entered, verified, and archived at a contract research organization (CRO) external to Lilly and/or at Lilly. Data listings, summaries, and analyses will be performed by a CRO and/or by Lilly under the guidance and approval of statisticians at Lilly. Statistical analysis of this study will be the responsibility of Lilly.

Any change to the data analysis methods described in the protocol will require an amendment ONLY if it changes a principal feature of the protocol. Any other change to the data analysis methods described in the protocol, and the justification for making the change, will be described in the statistical analysis plan and/or in the clinical study report (CSR). Additional exploratory analyses will be conducted, as deemed appropriate.

The patient populations used in the study are described below:

1. All Patients Entered: all patients who entered this study and completed Visit 1.
2. All Randomized: all patients who were randomized to a treatment arm.
3. Full Analysis Set (FAS): based on the intent to treat (ITT) principle, all patients who were randomized and who have taken at least one dose of study medication. Patients are assigned to the treatment arm to which they were randomized.
4. Per-protocol (PP): patients in the FAS/ITT population who also meet the following criteria:
 - a. violate no inclusion or exclusion criteria
 - b. have not discontinued from the study prior to 24 weeks
 - c. have not been off study medication for more than 10 consecutive days during the treatment period
 - d. have not received chronic (lasting longer than 14 consecutive days) systemic glucocorticoid therapy (excluding topical, intra-articular, intraocular, and inhaled preparations)

Unless otherwise specified, listings will be prepared using all randomized patients. Efficacy and safety analyses will be conducted using the FAS population. Selected analyses will be conducted using the All Randomized population and the PP population.

Unless otherwise noted, all tests of treatment effects will be conducted at a 2-sided alpha level of 0.05, and confidence intervals (CIs) will be calculated as 2-sided 95% CIs. All tests of interactions between treatment groups and other factors will be conducted at a 2-sided alpha level of 0.05. No adjustments for multiplicity will be performed. See Section 5.2.7 for the gate-keeping strategies used for primary/secondary endpoints.

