For patients with TEAR, a visit-wise listing of total and cross-reactive insulin antibody percent binding and clinical outcomes (HbA_{1c}, total hypoglycemia rate, basal insulin dose (U/Day, U/kg/Day), TEAE preferred terms) will be presented. The listing will be sorted by treatment and endpoint total insulin percent binding.

Incidence tables showing the number and percent of patients with initial and continuing TEAR at each visit will be presented. Similar analyses will be performed for the detection of total insulin antibodies and for the detection of cross reactive insulin antibodies.

Box plots of clinical outcomes (HbA_{1c}, total hypoglycemia rate, basal dose) will be generated by treatment and TEAR status.

In addition, the following patient listings of insulin antibodies (percent binding) will be provided for patients with TEAR: a listing of level of total insulin antibody percent binding across visit sorted by treatment and maximum postbaseline percent binding; a listing of level of total insulin antibody percent binding across visit sorted by treatment and endpoint percent binding. Similar listings will be presented for cross reactive percent binding.

In addition, the potential impact of total insulin antibody level and TEAR status on clinical response will be evaluated in several ways:

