1. The relationship between the natural logarithm of the last observed insulin antibody levels (Ln[antibody level]) and selected clinical response variables (efficacy and safety measures (eg HbA_{1c}, total hypoglycemia rate, basal dose [U/day, U/kg/day], total dose [U/day, U/kg/day], premeal dose [U/day, U/kg/day]) will be evaluated using scatterplots and analyzed using ANCOVA on efficacy/safety measure as the dependent variable with treatment, pre-study treatment (Lantus®-bolus, other basal-bolus, premixed insulin), and pre-study metformin or acarbose usage (metformin only, acarbose only, or neither) as fixed effects; baseline HbA_{1c} level, Ln(antibody level) and treatment-by-Ln(antibody level) interaction as covariates for the FAS patients with detectable antibodies postbaseline and with valid antibody testing at baseline (detected, ND). A significant treatment-by-insulin antibody interaction may be indicative of a differential treatment effect necessitating further exploration to determine the nature of the interaction. Only patients with non-missing baseline value and at least one non-missing post-baseline value of the clinical response variable will be included in the analysis.
2. The relationship between TEAR and selected clinical response variables (efficacy and safety measures (e.g. HbA_{1c}, total hypoglycemia rate, basal dose [U/day, U/kg/day], total dose [U/day, U/kg/day], premeal dose [U/day, U/kg/day]) will be analyzed using ANCOVA on efficacy/safety measure as the dependent variable with treatment, TEAR (yes/no), pre-study treatment (Lantus®-bolus, other basal-bolus, premixed insulin), and pre-study metformin or acarbose usage (metformin only, acarbose only, or neither) , treatment-by-TEAR interaction as fixed effects and baseline HbA_{1c} level as a covariate for the FAS patients with detectable antibodies postbaseline and with valid antibody testing at baseline (detected, ND). A significant treatment-by-TEAR interaction may be indicative of a differential treatment effect necessitating further exploration to determine the nature of the interaction. Only patients with non-missing

baseline value and at least one non-missing post-baseline value of the clinical response variable will be included in the analysis.

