3. The relationship between TEAR and overall incidence of categories of adverse events (TEAE, SAE, TEAE related to study drug, special topic allergic reactions, injection site reactions) will be assessed by showing the proportion of patients with an event for TEAR and non-TEAR patients by treatments for the FAS. For patients with and without TEAR, treatments will be compared using the Mantel-Haenszel test and the odds ratio and p-value from this test will be reported. The homogeneity of the odds ratios for TEAR and non-TEAR patients will be assessed using the Breslow-Day test.

The potential impact of cross-reactive antibody formation on clinical response similar to the analyses above will be done if there is sufficient number of patients with cross-reactive antibodies.

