For each subgroup listed above, the change in weight from baseline to 24-week will be analyzed using the same methodology as the subgroup analysis of HbA_{1c}.

Additional subgroup analyses will be carried out on selected safety outcomes:

- a) total, severe or nocturnal hypoglycemia at 24-week endpoint and for the overall 24-week period (rates and incidence)
- b) treatment-emergent antibody response (TEAR) at 24-week endpoint and for the overall 24-week period
- c) detectable insulin antibodies at 24-week endpoint and for the overall 24-week period
- d) categories of adverse events:
 - treatment-emergent adverse events (TEAEs) (overall incidence and preferred terms with $> 5\%$ incidence)
 - TEAEs related to study drug (overall incidence)
 - special topic assessment of allergic events (overall incidence)
 - injection site reactions (overall incidence)
 - serious adverse events (overall incidence)

For rates and incidence of hypoglycemia (total, nocturnal, severe) and categories of adverse events, the same set of 11 subgroups used to analyze change in HbA_{1c} and change in weight will be analyzed.

For each categorical safety outcome and subgroup listed above, the proportion of patients with an event will be compared between treatments for the FAS. Within each subgroup, treatments will be compared using the Mantel-Haenszel test and the odds ratio and p-value from this test will be reported. The homogeneity of the odds ratios across subgroups will be assessed using the Breslow-Day test.

For the 11 subgroups listed above, the rate of total, severe or nocturnal hypoglycemia per year at the 24-week endpoint and for the overall 24-week period will be analyzed. Within each subgroup, treatments will be compared using the negative binomial (NB) model with treatment as the only factor. The NB mean for each treatment and their ratio with corresponding 95% confidence interval will be presented. Additionally, within each subgroup the rates will be compared using the Wilcoxon test. The significance of the subgroup-by-treatment interaction will be evaluated using a negative binomial model with factors treatment, subgroup and treatment-by-subgroup interaction. The negative binomial model will be implemented using the SAS PROC GENMOD with natural logarithm of exposure time (in days) as an offset variable. The above subgroup analysis will be performed and p-values will be provided if there are at least a total of 20 events in the combined treatment groups.

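### SAP 5.2.11.4 item 3 aims to relate antibody response (TEAR) to adverse events, but its only formal tests compare the two insulins; no TEAR versus non-TEAR estimate is specified

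*SAP*

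**What the plan says.** SAP 5.2.11.4 introduces three analyses with a common purpose: "the potential impact of total insulin antibody level and TEAR status on clinical response will be evaluated in several ways".

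Item 3 takes up safety events. Its subject is "The relationship between TEAR and overall incidence of categories of adverse events", the categories being TEAEs, SAEs, drug-related TEAEs, special topic allergic reactions and injection site reactions. The relationship "will be assessed by showing the proportion of patients with an event for TEAR and non-TEAR patients by treatments for the FAS".

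Two formal steps follow. The first, whose results go into the report: "For patients with and without TEAR, treatments will be compared using the Mantel-Haenszel test and the odds ratio and p-value from this test". The second: "The homogeneity of the odds ratios for TEAR and non-TEAR patients will be assessed using the Breslow-Day test".

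Item 2 of the same list handles TEAR differently. It specifies "ANCOVA on efficacy/safety measure as the dependent variable with treatment, TEAR (yes/no), pre-study treatment" and further terms, including a treatment-by-TEAR interaction. Its example outcomes are HbA1c, total hypoglycemia rate and insulin doses. It is restricted to FAS patients with detectable antibodies after baseline and a valid baseline test.

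**The concern.** The stated question is whether patients who develop TEAR have more adverse events. In both formal steps, treatment is the factor compared and TEAR is the stratum. The Mantel-Haenszel odds ratio is LY2963016 versus Lantus, and Breslow-Day asks whether that treatment odds ratio differs by TEAR status. This is so whether the Mantel-Haenszel test is run separately in each TEAR group or pooled across them; the wording allows either.

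If TEAR raises AE risk by the same factor in both arms, the treatment odds ratios stay at 1 and the planned p-values are null. Such a pattern is plausible: the protocol's Introduction says the two products share a primary amino acid sequence and had similar safety profiles in the earlier type 1 diabetes study. The report would then carry null p-values under an aim that names TEAR and adverse events, and a reader could take them as evidence that TEAR has no bearing on AEs.

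**Working it through.** **Trial size.** Item 3 states no figure, so the planned sample size sets the scale. Inputs from SAP 5.1.1: margin 0.40, SD 1.05, two-sided 0.05, 80% power, 15% dropout.

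- Completers per arm: 2 × (1.960 + 0.842)² × 1.05² / 0.40² = 2 × 7.849 × 1.1025 / 0.16 = 108.2, so 109 (power 80.3%).
- Randomized per arm: 109 / 0.85 = 128.2, so 129.

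Both agree with the plan.

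**Worked table.** The counts are assumed; the documents give neither TEAR prevalence nor AE risks. Each arm has 25 TEAR patients, 12 with an AE (48%), and 104 non-TEAR patients, 15 with an AE (14.4%).

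*As written (treatment compared, TEAR as stratum):*

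- TEAR stratum: (12 × 13) / (13 × 12) = 1.00.
- Non-TEAR stratum: (15 × 89) / (89 × 15) = 1.00.
- Mantel-Haenszel odds ratio 1.00, p = 1.00. Observed counts equal expected counts in each stratum (for example 25 × 24 / 50 = 12), so the Breslow-Day statistic is 0.

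*TEAR compared, treatment as stratum:*

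- Odds ratio in each arm, and Mantel-Haenszel: (12 × 89) / (13 × 15) = 1068 / 195 = 5.48.
- Per arm: expected 25 × 27 / 129 = 5.233; variance 25 × 104 × 27 × 102 / (129² × 128) = 3.362.
- Chi-square: (2 × (12 − 5.233))² / (2 × 3.362) = 27.2, p = 1.8 × 10⁻⁷.

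The same 258 patients give p = 1.00 for the planned question and p = 1.8 × 10⁻⁷ for the stated one.

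**Simulation.** 1,500 trials per row, 129 per arm, TEAR prevalence and AE risks equal in both arms (all assumed). Entries are the percentage of trials with p < 0.05, the level set in SAP 5.2.1 ("all tests of treatment effects will be conducted at a 2-sided alpha level of 0.05").

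| TEAR prevalence | AE risk, TEAR / non-TEAR | Planned Mantel-Haenszel | Planned Breslow-Day | TEAR vs non-TEAR, stratified by treatment |
|---|---|---|---|---|
| 10% | 15 / 15 | 4.3 | 3.7 | 5.2 |
| 10% | 30 / 15 | 6.4 | 5.1 | 47.1 |
| 10% | 45 / 15 | 4.7 | 4.2 | 92.1 |
| 10% | 60 / 40 | 5.6 | 5.7 | 50.9 |
| 20% | 15 / 15 | 5.1 | 5.7 | 4.3 |
| 20% | 30 / 15 | 5.6 | 5.7 | 68.4 |
| 20% | 45 / 15 | 5.0 | 4.9 | 99.2 |
| 20% | 60 / 40 | 4.5 | 4.8 | 72.6 |
| 30% | 15 / 15 | 5.4 | 5.9 | 4.9 |
| 30% | 30 / 15 | 4.8 | 5.7 | 77.1 |
| 30% | 45 / 15 | 4.3 | 5.5 | 99.9 |
| 30% | 60 / 40 | 4.4 | 4.7 | 84.7 |

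Where TEAR matters, the planned tests stay near 5%. Where it does not (15 / 15), the TEAR comparison also stays near 5%.

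**The interaction is already covered.** Let L and G be the odds of an AE on LY2963016 and Lantus, with subscript 1 for TEAR and 0 for non-TEAR. The ratio of treatment odds ratios, (L₁/G₁) / (L₀/G₀), equals the ratio of TEAR odds ratios, (L₁/L₀) / (G₁/G₀). Breslow-Day therefore tests the same null hypothesis whichever variable is the stratum. Only the TEAR main-effect odds ratio is missing.

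**The case against.** A reader might infer that the plan cannot reveal any TEAR effect on safety, or that such an effect would go unreported. The documents do not support that:

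- Item 3 commits to showing AE proportions for TEAR and non-TEAR patients by treatment. In the worked table, 48% against 14.4% would be visible in each arm.
- SAP 5.2.11.4 also lists TEAE preferred terms for patients with TEAR, and item 2 has a TEAR term with total hypoglycemia rate among its outcomes.
- Breslow-Day can respond if the TEAR effect differs between the insulins.

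The other side can also say that the trial's safety objective is to compare the two insulins, so a treatment-by-TEAR check is the relevant one. SAP 5.2.12 uses almost the same test sentence for subgroups: "Within each subgroup, treatments will be compared using the Mantel-Haenszel test and the odds ratio and p-value from this test will be reported". Protocol 12.2.9.1 promises only the relationship of antibody level with HbA1c, total hypoglycemia and basal dose, so item 3 already exceeds the protocol. TEAR also arises after randomisation and some AEs may precede it, so a p-value for TEAR could mislead, and SAP 5.2.15 leaves room for exploratory analyses.

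Much of this stands. It limits the point to the absence of a formal estimate for AE categories, and it requires the added odds ratio to be labelled as an association. It does not remove the mismatch. Item 3 names the TEAR–AE relationship as its own question, then attaches p-values to another one. Item 2 does not fill the gap, since it omits AE categories and is limited to patients with detectable postbaseline antibodies. The planned treatment comparisons within TEAR groups also condition on a postbaseline variable, so that caution applies to both analyses.

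**Conclusion.** The point holds as a gap in formal inference. For the AE categories in item 3, the SAP specifies no odds ratio, CI or p-value for TEAR versus non-TEAR. When the TEAR odds ratio is the same in both arms and TEAR is equally common in both, the planned tests reject at about the nominal rate whatever the size of that effect: 4.2% to 6.4% across the nine non-null scenarios, against 47% to 99.9% for the direct comparison. The power figures depend on assumed TEAR prevalence and AE risks. The structural result depends only on which factor is tested.

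The change is worth making, but its reach is limited. This is a supportive safety analysis. The primary noninferiority test, the gated secondary test and the overall between-arm AE comparisons do not depend on it.

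**What to change.** In SAP 5.2.11.4 item 3, keep the planned display of proportions and, for each AE category, add:

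- the TEAR versus non-TEAR odds ratio with 95% CI within each arm;
- a Mantel-Haenszel TEAR versus non-TEAR odds ratio with 95% CI, stratified by treatment.

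Retain Breslow-Day as the check for treatment-by-TEAR interaction. State in the SAP and in table footnotes that the TEAR odds ratio is a non-randomised association, because TEAR is acquired during treatment and some events may come before it. State also that the treatment comparisons within TEAR groups do not test the TEAR–AE relationship.

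The cost is a few lines of SAP text and one more run of the same procedure with row and stratum variables exchanged. No new data are needed.

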5.2.11.5. Vital Signs

Vital signs measures (systolic blood pressure, diastolic blood pressure, and heart rate) and their change from baseline will be summarized by descriptive statistics (mean, median, SD, standard error, minimum, and maximum) by visit for the FAS population.

In addition, the MMRM model will evaluate the change from baseline in vital sign measure as the dependent variable with treatment (LY2963016, Lantus®), pre-study treatment (Lantus®-bolus, other basal-bolus, premixed insulin), and pre-study metformin or acarbose usage (metformin only, acarbose only, or neither), visit, and interaction between visit and treatment as fixed effects; the baseline value of the vital sign measure and the baseline HbA_{1c} level as covariates; and a random effect for patient. The LSMMeans will be estimated using the observed margins (OM) option in SAS MIXED procedure.

The number and percentage of patients with treatment-emergent outlier vital sign measures at each post baseline visit will be presented and analyzed using Fisher's exact test or Pearson's chi-square test for systolic blood pressure, diastolic blood pressure, and pulse rate according to the categories as listed below:

- low systolic blood pressure (≤ 90 mmHg and a decrease from baseline ≥ 20 mmHg)
- high systolic blood pressure (≥ 140 mmHg and an increase from baseline ≥ 20 mmHg)
- low diastolic blood pressure (≤ 50 mmHg and a decrease from baseline ≥ 10 mmHg)
- high diastolic blood pressure (≥ 90 mmHg and an increase from baseline ≥ 10 mmHg)
- low heart rate (< 50 bpm and a decrease from baseline ≥ 15 bpm)
- high heart rate (> 100 bpm and an increase from baseline ≥ 15 bpm)

5.2.11.6. Other Safety Measures

Exposure:

Exposure to each treatment during the treatment period of the study will be calculated for each patient and summarized by treatment group. Exposure will be calculated as the number of days

from the date of first dose of the study drug (or if this information is missing, from the date of randomization) to the date of last treatment dose. Exposure will be expressed in days, months (30 days) and years (365.25 days).

Listings of Hepatic Disorders and Abnormal Liver Enzymes:

A listing will be provided for patients with pre-existing conditions or treatment emergent adverse events in the following MedDRA SMQs for Hepatic Disorders (Broad and Narrow SMQ):

Narrow	Biliary disorders	20000118
Narrow	Drug-related hepatic disorders – comprehensive	20000006

Additionally listings will be provided for all patients who meet at least one of the following liver enzyme outlier criteria for at least one visit: ALT >3 ULN, AST >3 ULN, total bilirubin >2 ULN, or alkaline phosphatase >2 ULN at any visit. These listings will include all liver enzymes at all visits.

Listings Based on Renal Function:

Listings will be provided for patients with severe reduction in GFR or kidney failure at any visit according to the following criteria:

Severe reduction in eGFR (15-29 mL/min/1.73 m²)
Kidney Failure (eGFR < 15 mL/min/1.73 m²).

These listings will include all estimated GFR (eGFR) at all visits.

5.2.12. Subgroup Analyses

The consistency of the treatment effect for the change in HbA_{1c} level will be assessed in the following subgroups in the FAS population if there are sufficient numbers of patients in each treatment by subgroup (e.g. 20 patients per cell):

- Entry HbA_{1c} levels (<7%, ≥7%)
- Entry HbA_{1c} levels (<8.5%, ≥8.5%)
- Pre-study treatment (Lantus[®]-bolus, other basal-bolus, premixed insulin)
- Entry BMI (<30, ≥30)
- Entry BMI (<25, ≥25)
- Entry age (<65, ≥65)
- Entry age (<75, ≥75)
- Gender
- Prestudy metformin or acarbose use (metformin only, acarbose only or neither)
- Time of basal insulin injection (daytime, evening/bedtime)
- Renal function, as estimated by estimated glomerular filtration rate (EGFR) using the MDRD formula (see [Appendix 2](#)). The following EGFR categories will be used:

- normal or increased GFR: EGFR (≥ 90 mL/min/1.73 m²)
- mild reduction in GFR: EGFR (60 to 89 mL/min/1.73 m²)
- Moderate reduction in GFR: EGFR (30 to 59 mL/min/1.73 m²)
- Severe reduction in GFR: EGFR (15 to 29 mL/min/1.73 m²)
- Kidney failure: EGFR (< 15 mL/min/1.73 m²).

The categories severe reduction in GFR and kidney failure will be combined if there are fewer than 20 patients in either of these categories.

The change in HbA_{1c} from baseline to 24-week endpoint will be analyzed using MMRM with treatment, visit, prestudy treatment, prestudy metformin or acarbose usage, subgroup, subgroup-by-treatment interaction, subgroup-by-visit interaction, treatment-by-visit interaction, and treatment-by-visit-by-subgroup interaction as fixed-effects, the baseline value of HbA_{1c} as a covariate, and a random effect for patient for the FAS population. If the subgroup is one of the stratification variables, then the subgroup will only be included once in the model. A significant treatment-by-subgroup interaction ($p < .05$) may be indicative of a differential treatment effect across levels of the subgroup, necessitating further exploration of the nature of the interaction.

The contrast from the MMRM model with the OM option using PROC Mixed in SAS above will be used to obtain the LSmeans for change in HbA_{1c} levels from baseline to Week 24 within each treatment at each level of the subgroup. Additionally, the difference of these LSmeans between treatment groups with 95% confidence interval and p-values will be presented.

For each subgroup listed above, the change in weight from baseline to 24-week will be analyzed using the same methodology as the subgroup analysis of HbA_{1c}.

Additional subgroup analyses will be carried out on selected safety outcomes:

- a) total, severe or nocturnal hypoglycemia at 24-week endpoint and for the overall 24-week period (rates and incidence)
- b) treatment-emergent antibody response (TEAR) at 24-week endpoint and for the overall 24-week period
- c) detectable insulin antibodies at 24-week endpoint and for the overall 24-week period
- d) categories of adverse events:
 - treatment-emergent adverse events (TEAEs) (overall incidence and preferred terms with $> 5\%$ incidence)
 - TEAEs related to study drug (overall incidence)
 - special topic assessment of allergic events (overall incidence)
 - injection site reactions (overall incidence)
 - serious adverse events (overall incidence)

For rates and incidence of hypoglycemia (total, nocturnal, severe) and categories of adverse events, the same set of 11 subgroups used to analyze change in HbA_{1c} and change in weight will be analyzed.

For each categorical safety outcome and subgroup listed above, the proportion of patients with an event will be compared between treatments for the FAS. Within each subgroup, treatments will be compared using the Mantel-Haenszel test and the odds ratio and p-value from this test will be reported. The homogeneity of the odds ratios across subgroups will be assessed using the Breslow-Day test.

For the 11 subgroups listed above, the rate of total, severe or nocturnal hypoglycemia per year at the 24-week endpoint and for the overall 24-week period will be analyzed. Within each subgroup, treatments will be compared using the negative binomial (NB) model with treatment as the only factor. The NB mean for each treatment and their ratio with corresponding 95% confidence interval will be presented. Additionally, within each subgroup the rates will be compared using the Wilcoxon test. The significance of the subgroup-by-treatment interaction will be evaluated using a negative binomial model with factors treatment, subgroup and treatment-by-subgroup interaction. The negative binomial model will be implemented using the SAS PROC GENMOD with natural logarithm of exposure time (in days) as an offset variable. The above subgroup analysis will be performed and p-values will be provided if there are at least a total of 20 events in the combined treatment groups.

For TEAR at 24 weeks endpoint and overall, subgroup analyses will be performed only for pre-study treatment (Lantus®-bolus, other basal-bolus, premixed insulin), entry age (>65 , ≤ 65), entry age (<75 , ≥ 75) and renal function. For detectable antibodies at 24 weeks endpoint and overall, subgroup analyses will be performed only for pre-study treatment (Lantus®-bolus, other basal-bolus, premixed insulin).

Other subgroup analyses may be performed if deemed appropriate as exploratory analyses.

